### **Main Eligibility Criteria:**

- Male or female subjects  $\geq 18$  years of age with a known diagnosis of DM and active disease.
- Must meet one of the following for DM diagnosis:
  1. Bohan and Peter's criteria for probable or definite DM ([Bohan and Peter, 1975a](#); [Bohan and Peter 1975b](#))
  2. ACR/EULAR criteria ([Lundberg et al, 2017](#))
- Must meet one of the following for disease activity / severity:
  - i. MDGA  $\geq 3$  cm (0 – 10 cm scale) and MMT-8 score  $\leq 142$  (out of 150 total possible)
  - ii. Sum of MDGA, PtGA and EMGA VAS scores is  $\geq 10$  cm (all scales individually on 0-10 cm scale)
  - iii. MDGA  $\geq 3$  cm and CDASI activity score of  $> 14$

Doses of non-corticosteroid immunosuppressant medications should be stable for  $\geq$  8 weeks at screening. Doses of oral corticosteroids should be stable for  $\geq$  4 weeks at Visit 1.

**Phase: 3**

**Study Sites:** Up to approximately 75 sites in North American, European, and Asian Pacific regions.

**Study Treatment:**

All treatments: lenabasum (20 mg or 5 mg) or placebo, will be administered orally BID for up to 52 weeks.

**Study Duration:** Estimated duration for Part A is anticipated to be approximately 36 months from first subject first visit to last subject last visit and will depend on the rate of enrollment across the various sites.

**Statistical Methodology:** It is planned that about 150 subjects will be dosed at a ratio of 2:1:2 to lenabasum 20 mg, lenabasum 5 mg, or placebo arms, respectively, with a total of 120 subjects expected to complete the study (assuming  $\sim$  20% drop out rate). A total of 120 subjects (48 subjects each in the 20 mg BID and placebo groups, and 24 subjects in the 5 mg BID dose group) achieves 95% power to detect a significant difference in the TIS score between the lenabasum 20 mg BID group and placebo. This assumes a two-sided test at alpha = 0.05 and a common standard deviation of 20.00 in both treatment arms for the primary efficacy outcome, and a difference in the TIS between lenabasum 20 mg BID and placebo of 15.0. The number of subjects to be randomized may be adjusted further during the study after a blinded interim analysis of the emerging data. The intent is to perform a blinded interim examination of the variance of the TIS to potentially increase the sample size to maintain power (with no statistical adjustment to the alpha level required). The projected maximum number of subjects to be randomized is about 230 subjects (for 183 completers), which corresponds to standard deviation of 30.00, and 85% power.

Randomization will be stratified based on screening MMT-8 score ( $< 135$  or  $\geq 135$ ), prednisone dose ( $\leq 10$  mg or  $> 10$  mg per day or equivalent), and region (US vs. ex-US). The primary efficacy variable is the TIS. The primary analysis is to compare the TIS at Week 28 between the lenabasum 20 mg BID treated group and the placebo group using a mixed model for repeated measures (MMRM). The model will have TIS score as a dependent variable, treatment, visit, treatment\*visit interaction as factors, Baseline MMT-8 score, prednisone use, and region as covariates, and subject as the repeated random effect using an unstructured covariance matrix. Two-sided p-values and 95% confidence intervals associated with the least-square (LS) mean difference between the lenabasum group and placebo will be presented for each visit. If the distribution of the TIS score does not meet the assumptions of normality, a nonparametric analysis may be performed (e.g., MMRM analysis on the ranked data).

Continuous secondary and tertiary outcome variables will be analyzed similarly to the primary MMRM model, using change from Baseline as the dependent variable, with the Baseline of each endpoint also included in the model. Other outcomes based on the proportion of subjects achieving defined criteria will be analyzed using a Fisher's exact or Cochran-Mantel-Haenzel test.

All primary and secondary efficacy analyses will be two-sided at the 0.05 significance level. The overall Type I error rate will be controlled for the primary and secondary efficacy outcomes with independent hierarchical assessments of efficacy at each comparison of lenabasum to placebo. The order of the tests for treatment effect will be as follows:

- Primary efficacy outcome (at Week 28): TIS, lenabasum 20 mg BID versus placebo. Change from baseline in each core set measure of the composite TIS will be presented to support the TIS: MDGA; PtGA; MMT-8; HAQ; muscle enzymes; EMGA
- Secondary efficacy outcomes (Change from Baseline or proportion of subjects at Week 28, unless otherwise specified). The list will be done in order below for comparisons between lenabasum 20 mg BID and placebo cohorts:
  - Subjects who achieve DOI
  - Subjects who improve by at least one category on the IGA scale of skin activity
  - Subjects who achieve TIS  $\geq 40$  (at least moderate improvement)
  - TIS in subjects receiving any immunosuppressant medication for  $> 1$  year at Baseline
  - TIS at Visit 10 (Week 52)
  - CDASI activity score

The list will continue in order below for comparisons between lenabasum 5 mg BID and placebo cohorts:

- TIS
- Subjects who achieve DOI
- Subjects who improve by at least one category on the IGA scale of skin activity
- Subjects who achieve TIS  $\geq 40$  (at least moderate improvement)
- TIS in subjects receiving any immunosuppressant medication for  $> 1$  year at Baseline
- TIS at Visit 10 (Week 52)
- CDASI activity score

Note that statistical significance within an endpoint must be achieved to continue in the assessment of the next endpoint.

No formal statistical testing will be performed to compare the safety in lenabasum versus placebo cohorts. The number and percentage of subjects with AEs will be summarized for each treatment by system organ class and preferred term. Similar summaries will be presented for AEs related to study product, AEs leading to permanent discontinuation of study product, SAEs, and AEs resulting in death. Any AE with a relationship category of possible, probable, or definite is considered related to study product. The AEs will be coded using the Medical Dictionary for Regulatory Activities (MedDRA). All reported AEs will be provided in separate data listings. Descriptive statistics will be used to summarize clinical laboratory parameters, vital signs and their corresponding change from Baseline for each treatment by scheduled timepoint.

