### **Part A Double-Blind, Placebo Controlled Phase**

The initial plan is for approximately 150 dosed subjects to receive at least 1 dose of study product. The final number of subjects to be dosed will be decided after a blinded interim analysis. The timing and methods for the interim analyses will be outlined in the statistical analysis plan (SAP). It is expected that approximately 200 subjects will be screened to dose 150 subjects. Subjects will be randomized to receive lenabasum 20 mg, lenabasum 5 mg, or placebo twice-daily (BID) in a 2:1:2 ratio. It is hypothesized that subjects receiving lenabasum will have greater improvement in the TIS score (2016 ACR/EULAR Myositis Response Criteria) at Week 28 compared to subjects receiving placebo.

The total duration of participation for an individual subject is approximately 60 weeks and includes the following: a screening visit (up to 4 weeks before Visit 1), up to 52-week treatment period, and a Safety Follow-up Visit that will be conducted  $4 \pm 1$  weeks after the last visit. Subjects will be assessed for safety and efficacy parameters every 6 weeks (except for Visit 2, which will occur 4 weeks after Visit 1) for a total of up to 10 treatment visits. Study personnel will also contact subjects by telephone halfway between Visit 9 and Visit 10 (Week  $49 \pm 1$ ) to assess compliance, safety and overall status of DM, if applicable.

A subject's corticosteroid or other immunosuppressant treatments may be reduced if the investigator determines that clinical improvement in the subject's dermatomyositis has occurred and a reduction is warranted. It is recommended that a reduction in corticosteroid or immunosuppressant treatment should not occur before Visit 4 or after Visit 8. A preferred schedule for reduction is provided in [Section 5.5.1](#) of the protocol.

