#### **9.4.1.2. Adjustments for Multiplicity**

The overall type I error rate will be controlled for primary and secondary outcomes with a hierarchical ordering of assessments. The order of the tests for treatment effect will be as follows:

- Primary efficacy outcome: Mean TIS, lenabasum 20 mg BID versus placebo, at Week 28.
- Secondary efficacy outcomes (Change from Baseline at Week 28):

The following endpoints will be compared in lenabasum 20 mg BID compared to placebo cohorts and lenabasum 5 mg BID compared to placebo cohorts at Week 28. All outcomes involving continuous variables will be assessed as absolute values and, if relevant, change from Baseline. All categorical variables will be assessed as number and proportion of subjects in each category. The list will be done in order below for comparisons between lenabasum 20 mg BID and placebo cohorts:

- Subjects who achieve DOI
- Subjects who improve by at least one category on the IGA scale of skin activity
- Subjects who achieve TIS  $\geq 40$  (at least moderate improvement)
- TIS in subjects receiving any immunosuppressant medication for  $> 1$  year at Baseline
- TIS at Week 52
- CDASI activity score

The list will continue in order below for comparisons between lenabasum 5 mg BID and placebo cohorts:

- TIS
- Subjects who achieve DOI Subjects who improve by at least one category on the IGA scale of skin activity
- Subjects who achieve TIS  $\geq 40$  (at least moderate improvement)
- TIS in subjects receiving any immunosuppressant medication for  $> 1$  year at Baseline
- TIS at Week 52
- CDASI activity score

Note that, in Part A, statistical significance for each endpoint must first be achieved in order to continue in the assessment of the next endpoint, following the testing sequence above.

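### The synopsis describes type I error control by independent hierarchies per dose, but its own test list and section 9.4.1.2 set one gated sequence from 20 mg to 5 mg

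*Protocol*

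**What the plan says.** The Protocol states the multiplicity rule twice.

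**Synopsis, Statistical Methodology.** The level is set first: "All primary and secondary efficacy analyses will be two-sided at the 0.05 significance level". The next sentence claims control of the overall type I error for the primary and secondary outcomes by means of "independent hierarchical assessments of efficacy at each comparison of lenabasum to placebo". A test order follows: TIS at Week 28 for 20 mg against placebo, then six 20 mg secondary outcomes. It goes on: "The list will continue in order below for comparisons between lenabasum 5 mg BID and placebo cohorts", with seven 5 mg outcomes beginning with TIS. The gate closes the list: "statistical significance within an endpoint must be achieved to continue in the assessment of the next endpoint".

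**Section 9.4.1.2, Adjustments for Multiplicity.** "The overall type I error rate will be controlled for primary and secondary outcomes with a hierarchical ordering of assessments". The same outcomes appear in the same order, with the 5 mg list again introduced as a continuation of the 20 mg list. The gate here is that "statistical significance for each endpoint must first be achieved in order to continue in the assessment of the next endpoint", and the sentence ends by tying this to the testing sequence just given. The word *independent* does not appear.

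**The concern.** There are two comparisons of lenabasum with placebo, one per dose. Hierarchies that are independent by comparison would each start at full alpha, and the 5 mg chain would not wait for the 20 mg chain. In a single continuing sequence it must wait. The two descriptions part company as soon as any 20 mg test fails: under the first, the 5 mg tests go ahead at 0.05; under the second, they have no confirmatory standing.

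The synopsis gate does not settle the matter cleanly. It speaks of significance within an endpoint and of moving to the next endpoint. The first 5 mg test is TIS at Week 28, the same endpoint as the 20 mg primary, so the wording leaves room to argue that a failed 20 mg test does not block it. Only section 9.4.1.2 ties the gate expressly to the listed sequence.

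At stake are the status of any 5 mg claim and the accuracy of the sentence that asserts error control. If the reading were chosen after unblinding, the choice could depend on the results.

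**Working it through.** **Inputs, all from the Protocol**
- Each test at two-sided 0.05 (Synopsis), critical value 1.96.
- Allocation: "Subjects will be randomized to receive lenabasum 20 mg, lenabasum 5 mg, or placebo twice-daily (BID) in a 2:1:2 ratio".
- Expected completers 48 (20 mg), 24 (5 mg), 48 (placebo) (Synopsis). The dosed numbers 60/30/60 in section 9.2 give the same correlation.
- Superiority is claimed only for a positive difference (section 9.1.1).

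**Number of tests.** For 20 mg, TIS plus six secondaries makes 7. For 5 mg there are 7: TIS, DOI, IGA, TIS of at least 40, TIS in the subgroup on immunosuppressants for more than a year, TIS at Week 52, and CDASI activity. The total is 14. (Section 9.4.1.2 runs the 5 mg DOI and IGA items together on one line; they are counted as two, as in the synopsis.)

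**Step 1: the plan's own figure, 5%.** In one fixed sequence, nothing is rejected unless the first test rejects. Under the global null the family-wise error is therefore that of the first test, 0.05. A simulation of 4 million trials gives 0.0499. The stated control is reproduced for the listed sequence.

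**Step 2: two separate chains.** Under the global null, a false rejection occurs if either chain's first test rejects. Both first tests are TIS at Week 28 and share the placebo arm:

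rho = (1/48) / sqrt[(1/48 + 1/48) × (1/48 + 1/24)] = 0.02083 / sqrt(0.04167 × 0.0625) = 0.408

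Family-wise error = 1 − P(|Z1| ≤ 1.96 and |Z2| ≤ 1.96) = 0.0931 with rho = 0.408 (simulation 0.0930).

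**Step 3: range and direction**

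| Case | Family-wise error |
|---|---|
| One sequence, two-sided | 5.0% |
| Two chains, rho = 0.408, two-sided | 9.3% |
| Two chains, uncorrelated: 1 − 0.95² | 9.75% |
| Two chains, Bonferroni bound | 10% |
| One sequence, false superiority claims only | 2.5% |
| Two chains, rho = 0.408, false superiority claims only | 4.65% |

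**Step 4: how often the readings could differ.** The Protocol gives power only for the first test (95%). As an assumption for illustration, let each of the other six 20 mg tests have 80% power. The chance of passing all seven is 0.95 × 0.8⁶ = 0.25 if they are independent, and at most 0.80 if fully correlated. On that assumption the 20 mg chain breaks before 5 mg in 20% to 75% of trials. In those trials the readings disagree on whether 5 mg may be tested, though not necessarily on whether it would succeed.

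**The case against.** The strongest reply is that the operative procedure is clear. Immediately after the disputed sentence, the synopsis announces an order of tests, prints one list, says that this list continues into the 5 mg comparisons, and attaches a gate. Section 9.4.1.2 prints the same list and a clearer gate. No sentence says that 5 mg testing starts afresh if 20 mg fails. The disputed sentence itself promises overall error control, which two full-alpha chains would not deliver, so a sympathetic reader would discount the word *independent*.

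Most of this stands. A reader might infer from the quoted phrase that the synopsis as a whole sets a different rule from section 9.4.1.2, and that the trial's family-wise error is 9.3%. The documents do not support that: the synopsis's own list agrees with section 9.4.1.2, and 9.3% follows only if one phrase overrides the list and the gate.

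What the reply does not remove is the contradiction. The sentence that explains how error is controlled names a method that does not control it, and the synopsis gate is too loosely worded to overrule that sentence beyond argument. Nor is this a detail left to the SAP: the Protocol states the rule itself, and a later document cannot make both statements true.

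**Conclusion.** The point holds as an internal inconsistency in the synopsis, not as a demonstrated inflation of alpha. The listed sequence, in the synopsis and in section 9.4.1.2, holds the family-wise error at 5%. The literal reading of the disputed sentence would allow 9.3% two-sided, or 4.65% against 2.5% counting only false superiority claims. Those figures assume the global null, normal test statistics, 2:1:2 allocation and full alpha for each dose. If the first true nulls in the two chains are less correlated, the two-sided figure moves towards 9.75%. The practical consequence is confined to trials in which at least one 20 mg test fails, where the formal status of the 5 mg tests would be open to dispute.

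**What to change.** Before unblinding, make two edits to the Synopsis, Statistical Methodology:

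1. Replace "independent hierarchical assessments of efficacy at each comparison of lenabasum to placebo" with: *a single fixed sequence of 14 tests (seven for lenabasum 20 mg versus placebo, then seven for lenabasum 5 mg versus placebo), each at two-sided 0.05, stopping at the first non-significant result*.
2. Replace the synopsis gating note with the gating sentence of section 9.4.1.2, including its reference to the listed sequence, so that both places carry the same rule.

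Section 9.4.1.2 needs no change of substance. The edits require no additional patients and no new analysis. The only downside is that the 5 mg tests lose any claim to a separate alpha, which the listed sequence does not give them anyway.

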### **Part B Open-Label Extension Phase (Optional)**

Upon completing Part A treatment (Visit 10), at the investigator's discretion, consenting subjects may directly rollover into open-label treatment (Part B).

All subjects in the open-label extension (OLE) will receive lenabasum 20 mg BID.

The same efficacy and safety parameters described as primary and secondary objective for Part A will be evaluated in Part B as described in the SAP.

## ABBREVIATIONS

5-D itch	Five-dimension itch
AE	Adverse event
ARCI-M	Addiction research center inventory - marijuana
AUC	Area under the curve
AUC 0-24	Area under the curve from hour 0 - 24
BID	Twice daily
BP	Blood pressure
CB1	Cannabinoid type 1 receptor
CB2	Cannabinoid type 2 receptor
CDASI	Cutaneous dermatomyositis disease area and severity index
CF	Cystic fibrosis
CK	Creatine phosphokinase
CRO	Contract research organization
CSR	Clinical study report
DM	Dermatomyositis
DMC	Data monitoring committee
EC	Ethics Committee
ECG	Electrocardiogram
eCRF	Electronic Case Report Forms
EDC	Electronic data capture
EQ-5D	European quality of life 5-domain questionnaire
FACIT	Functional assessment of chronic illness therapy
FDA	Food and Drug Administration
FSH	Follicle stimulating hormone
FVC	Forced vital capacity
GCP	Good Clinical Practice
HAQ-DI	Health Assessment Questionnaire – Disability index
HIPAA	Health Insurance Portability and Accountability Act
HIV	Human immunodeficiency virus
H 0	Null hypothesis
H 1	Alternative hypothesis
IB	Investigator's Brochure
IC	Informed consent
ICF	Informed consent form
ICH	International Conference on Harmonization
IFN	Interferon
IL-1 $\beta$	Interleukin 1 $\beta$
IRB	Institutional Review Board
IWRS	Interactive web-based randomization system
LH	Luteinizing hormone
LMP	Last menstrual period
LPLV	Last patient last visit
LS	Least-squares means

MedDRA	Medical Dictionary for Regulatory Activities
MID	Minimal important difference
mITT	Modified intent-to-treat
MMRM	Mixed model for repeated measures
MMT	Manual muscle testing
MMT-8	Manual muscle testing-8
mRNA	Messenger ribonucleic acid
PK	Pharmacokinetics
PP	Per-protocol
QT	Measure of the time between the start of the Q wave and the end of the T
QTc	QT corrected
SAE	Serious Adverse Event
SAF	Safety population
SAP	Statistical Analysis Plan
SD	Standard deviation
SID	Subject identification number
SOA	Schedule of Assessments
SSc	Systemic sclerosis
SUSAR	Suspected unexpected serious adverse reaction
TEAE	Treatment-emergent adverse event
TIS	Total improvement score
UP	Unanticipated Problem
US	United States
VAS	Visual analog scale
WOCBP	Women of child-bearing potential

## 1. INTRODUCTION

Lenabasum (also known as JBT-101) is a novel, first-in-class “pro-resolving” small molecule cannabinoid type 2 receptor (CB2) agonist that is being developed for the treatment of inflammation and fibrosis in several diseases such as: dermatomyositis (DM), systemic sclerosis (SSc), systemic lupus erythematosus (SLE) and cystic fibrosis (CF).

### 1.1. Study Rationale

Results from the first-in-DM patient study (JBT101-DM-001) demonstrated improvement in the primary efficacy variable, Cutaneous Dermatomyositis Disease Area and Severity Index (CDASI) activity score, as well as numerous secondary efficacy measures. Lenabasum was shown to have a favorable safety profile in this DM study, consistent with previous clinical studies with lenabasum in patients with CF and SSc. Given the small sample size of study JBT101-DM-001 and exclusion of patients with active muscle disease, this present study is designed to assess the safety and efficacy of lenabasum in a larger, broader population of DM patients.

### 1.2. Background

Dermatomyositis is a severe autoimmune disease with distinctive cutaneous and muscle symptoms that are frequently accompanied by other manifestations. Although robust epidemiologic data are not available, it is estimated that < 13,500 to ~70,000 individuals in the United States (US) may have DM (Jacobson et al, 1997; Reeder et al, 2010). The most common age of onset is between 50-60 years of age (Tansley et al, 2013); however, DM has been observed in younger populations. Juvenile DM occurs before the age of 16 and has an incidence rate of around 1 case per 1 million children (Quartier et al, 2013).

Skin findings associated with DM include rashes characterized by erythema as well as pruritus of the scalp, face, dorsum of the hands, and upper back (Klein et al, 2007; Goreshi et al, 2011). Other manifestations of DM can include: muscle weakness (Bohan et al, 1977; Koh et al, 1993; Volochayev et al, 2012; Na et al, 2009); pulmonary complications (Kalluri et al, 2010; Ascherman et al, 2002); cardiac findings (Bazzani et al, 2010), esophageal involvement (de Merieux et al, 1983; Marie, 2012), joint disease (Marie, 2012), and associated malignancies (Hill et al, 2001; Yamasaki et al, 2011). Quality of life is significantly impacted in DM patients (Goreshi et al, 2011). Mortality in patients with DM is high with survival estimated to be 70% at 5 years and 57% at 10 years (Schiopu et al, 2012).

The clinical presentation of DM is a result of underlying, unresolved chronic inflammation. Classic inflammatory mediators include activated immune cells and proinflammatory cytokines such as tumor necrosis factor  $\alpha$  (TNF $\alpha$ ), interleukin 1 beta (IL-1 $\beta$ ), and type 1 interferons (IFNs) (Wong et al, 2012; Kim et al, 2012; Nabatian et al, 2012). Consequently, the current standard of care for DM includes the use of corticosteroids. Long-term systemic use of corticosteroids has shown to be associated with a number of adverse events (AEs) such as: osteoporosis and fractures; adrenal suppression; hyperglycemia and diabetes; cardiovascular disease and dyslipidemia, dermatological and gastrointestinal events; psychiatric disturbances; and immunosuppression (Liu et al, 2013). Side-effects of corticosteroid have been reported to affect 32% (Baron and Small, 1985) to 41% (Tymms and Webb, 1985) of treated patients with DM. In

long-term studies, disability associated with corticosteroid side-effects, especially osteonecrosis and osteoporotic vertebral fractures has also been reported ([Choy and Isenberg, 2002](#)).

If a patient is unresponsive to steroid therapy, i.e., no improvement after 3 - 6 months of prednisone, or if the patient relapses while tapering, a second-line immunosuppressive agent should be added ([Findlay et al, 2015](#)). Common second line choices include azathioprine ([Bunch et al, 1980](#)), methotrexate ([Newman et al, 1995](#)), and intravenous immunoglobulin ([Dalakas et al, 1993](#)). Other agents used in the treatment of DM are rituximab ([Oddis et al, 2013](#)), mycophenolate mofetil ([Pisoni et al, 2007](#)), tacrolimus ([Wilkes et al, 2005](#)), cyclosporine ([Qushmaq et al, 2000](#)), and cyclophosphamide ([Bombardieri et al, 1989](#)). Use of second line agents for their steroid-sparing effect is based on empirical data, and their use as a sole treatment may provide little benefit ([Dalakas, 2011](#)). In addition to lack of proof of efficacy ([Liu et al, 2013](#)), these second line immunosuppressive therapy agents are well known to be associated with significant side effects. Due to the severe side effects, reduction of immunosuppressive medication is an important goal for DM treatment.

Lenabasum is being developed as a therapy for the treatment of inflammation and fibrosis through the targeting of the CB2 receptor. CB2 is mainly distributed throughout immune cells ([Castaneda et al, 2013; Munro et al, 1993](#)). CB2 is expressed at 10- to 100-fold higher levels than cannabinoid type 1 (CB1) receptor on activated immune cells ([Carayon et al 1998; Galiegue et al, 1995; Munro et al, 1993](#)). Cell surface expression of CB2 returns to baseline levels once the immune response is resolved ([Carayon et al 1998](#)). As an agonist of CB2, lenabasum triggers a class switch of lipid mediators to favor pro-resolving lipid mediators which facilitate the transition of an active innate immune response back to an inactive response ([Shinohara et al, 2012; Zurier et al, 2009](#)).

Lenabasum has demonstrated potent pro-resolution (anti-inflammatory, anti-fibrogenic) effects in multiple non-clinical and clinical models (see [Sections 4 and 5](#) of the Investigator's Brochure).

A detailed description of the chemistry, pharmacology, efficacy, and safety of lenabasum is provided in the [Investigator's Brochure](#).

